9 PATIENTS

9.1 Description of recruitment procedures

Non-institutionalised healthy male or female subjects will be enrolled in the clinical trial. Recruitment may be accompanied by advertisement and patients may be contacted verbally, by telephone or in writing. Recruitment and inclusion of patients who are possibly dependent on the sponsor or an/the investigator and/or will have financial interests will be disclosed in any case.

9.2 Inclusion criteria

- Children (males/females), 6 - 12 years old, with severe acute tonsillitis.
- Possibility to initiate therapy within 72 hours since the onset of the disease symptoms.
- Score 4-5 according to Mclsaac Scale.
- Patient's and (or) one of his/her parents' willingness and ability to fulfil the requirements of the Study Protocol.
- Signed informed consent of the patient and (or) his/her parents for participation in the study.

9.3 Exclusion criteria

- Score -1 to 3 according to Mclsaac Scale.
- Indication for hospitalization, including:
 - o purulent complications (peritonsillar abscess and others);
 - o severe general condition.
- Indication for immediate initiation of systemic antibiotic therapy
- patients at risk of developing severe complications, including e.g. clinically relevant concomitant diseases of heart, lungs, kidneys, liver, neuromuscular apparatus, cancer diseases, immunosuppression, diabetes mellitus, cystic fibrosis.
- suspected infectious mononucleosis (by clinical signs);
- use of systemic antibacterial or antifungal agents, systemic glucocorticosteroids, cytostatics, immunomodulatory drugs, "interferons" or interferon derivatives during the last 14 days prior to inclusion;
- presence of haemorrhagic or pronounced necrotic process in oral cavity or pharynx, including the lymphoid ring.
- Intolerability or individual hypersensitivity to any of the study drug ingredients and the reference treatment scheme.

Patients who refuse to sign the informed consent or who do not agree to passing on of their pseudonymous data to the monitor / CRO, the sponsor, and competent national or European community authorities must not be included in this trial.

9.4 Premature discontinuation

9.4.1 Withdrawal criteria for included patients

Patients may prematurely discontinue their participation in the trial at any time, without giving reasons and without any disadvantageous consequences for their subsequent medical care.

Patients can be withdrawn from the trial by the investigator for the following reasons:

- Withdrawal of consent
- Serious Adverse Events (SAEs) at the Principal Investigator's discretion
- Appearance of non-tolerable AE(s)
- Appearance of an exclusion criterion, which concerns the safety of the patient in the opinion of the investigator
- non-adherence to the trial conditions or relevant deviations from procedures with regard to medical aspects at the Principal Investigator's discretion
- Diseases, AEs requiring treatment that occur after inclusion, which do not constitute SAEs but which, in the opinion of the Principal Investigator, would probably prevent achievement of the clinical trial objectives or which unacceptably endangered the safety of the subject
- Poor compliance of the patient
- Patient lost to follow-up
- Pregnancy (females of childbearing potential)
- Any situation judged by the investigator to be more harmful for the patient if he/she remains in the trial
- Other reasons which in the opinion of the investigator justify withdrawal of a patient (e.g. not meeting inclusion criteria during screening period)

In all cases, the reason for and date of withdrawal from the trial as well as the day and time of last intake of IMP must be recorded in the CRF and in the patient's medical records.

The investigator must make every effort to contact patients lost to follow-up. Attempts to contact such patients must be documented in the patient's records (e.g. times and dates of attempted telephone contact, documentation for sending a registered letter etc.).

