5 TRIAL SYNOPSIS

Trial code	ATi-2
Title of Trial	A Protocol of a Multicenter, Randomized, Open-Label, Comparative Study of Therapeutic Efficacy, Safety and Tolerability of Imupret application in the therapeutic concept of delayed prescription of antibiotics in children, aged 6-12 with severe acute tonsillitis.
Working title	Imupret in tonsillitis
Trial Design	open-label, exploratory, comparative, multicentre, randomized, prospective, parallel-group study.
Clinical phase	IV
Inclusion diagnosis	Acute tonsillitis
Trial objectives	
Assessment of the influence of Imupret (drops) prescriptions in the therapeutic concept of delayed prescription of antibiotics to:
 
 • need for antibiotics • regression of the tonsillitis symptoms • duration of antipyretics administration
Number of patients	approximately N=200 (1:1 ratio active treatment: reference)
Specialization of investigator	Head of Department of Otorhinolaryngology Head & Neck Surgery
Time schedule	Planned FPI (First patient in): approximately February 2019 Planned LPO (Last patient out): approximately December 2019
Efficacy endpoints	
The main criterion (main variable):
 
 - decrease in the severity of each symptom (complaint) that is part of the Mclsaac scale of tonsillitis manifestations, up to 1 point or less. This variable is dichotomous, with the categories "treatment effective" and "treatment not effective": - Treatment is effective - reducing the severity of each symptom (complaint) that is part of the Local Tonsillitis Manifestation Scale (0-15), of tonsillitis manifestations, up to 1 point or less in the evaluation stages. Absence of indications for prescribing antibacterial therapy - Treatment is not effective - the condition given for the category "therapy is effective" is not met.
Secondary end-points	
Secondary variables:
 
 - a decrease in the severity of the symptoms of the underlying disease, at the 2- nd, 3 -rd and 4- th visits compared to the 1- st visit. - decrease in the total score (the sum of scores for each symptom) according to the scale of local manifestations of tonsillitis at the 2-nd, 3-rd and 4-th visits in comparison with the 1-st visit. - a decrease in temperature in the armpit at the 2-nd and 3-rd visits compared to the 1-st visit. - a patient's self-assessment of the quality of life (every day). - Duration of NSAID administration. -Therapy compliance

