Safety evaluation	
 - Adverse events (AEs), serious adverse events (SAEs) - Incidence of adverse drug reactions (ADRs)

	
- Overall assessment of tolerability
												

Methodology
	
 1. Medical history, demographic and anthropometric data at screening. 2. Complaints, patient questioning by organs and systems – at each visit, including any unscheduled visit and telephone contact. 
All complaints are assessed using a 4-point rating scale, beginning from the visit at which the complaint was identified for the first time.
 
 3. Physical examination: skin and visible mucosa examination, palpation of abdomen and lymph nodes, oropharyngoscopy are performed at each visit including any unscheduled visit. 
Symptoms are assessed using a 4-point rating scale, beginning from the visit at which the symptom was identified for the first time.
 
 4. Evaluation of probability of acute bacterial tonsillitis in accordance to McIsaac scale (sum of scores) 
  
 McIsaac scale (sum of scores)	The probability of the identification of β-hemolytic streptococcus in a smear from pharynx	
   
 -1 or 0	1%	
 
 1	10%	
 
 2	~17%	
 
 3	~35%	
 
 4 or 5	~50%	
  
 
 5. Complaints included in the Local Tonsillitis Manifestations Scale are assessed at each visit including any unscheduled visits 6. Symptoms included in the Local Tonsillitis Manifestations Scale are assessed at each visit 7. Axillary temperature assessment at each visit including any unscheduled visits. 8. Clinical blood count, urinalysis and blood chemistry according to the investigator's decision. 9. Self-assessment of the patient's state of health by him/herself and (or) his/her parents using a visual analogue scale is performed on a daily basis. 	McIsaac scale (sum of scores)	The probability of the identification of β -hemolytic streptococcus in a smear from pharynx	-1 or 0	1%	1	10%	2	~17%	3	~35%	4 or 5	~50%

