8.3.3 Reference treatment

All patients of the trial will undergo the reference treatment described below. However, only one of the two study groups (study group 1) will receive and add-on treatment with either Imupret® oral solution (see 0 and 8.3.2).

Reference treatment comprises instructions for patient's behavior as well as possible medical treatment when needed:

- Sparing diet with fractional feeding (5-6 times a day) in only small portions explicitly excluding coarse, spicy, or heavily digestible food
- At the discretion of the investigator, elimination of all factors irritating pharyngeal mucosa (e.g. thermal, chemical influence etc.)

At the discretion of the investigator, Paracetamol as single doses up to 500 mg – not more than 3-4 times daily

- At the discretion of the investigator, topical treatment like benzydamine, lidocaine (in case of severe sore throat)
- At the discretion of the investigator, antibiotic treatment in case it is indicated with e.g. amoxicillin clavulanate, cephalosporins (in case of prescription of antibiotics patients will be evaluated separately)

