8.5 Time schedule and visits

Four scheduled visits will be performed during the first phase of the study:

First study phase

- 1 visit (1st day): screening, randomization and treatment; evaluation by Mc Isaac Score scale; LTM Scale (Local Tonsillitis Manifestation Scale): (5 symptoms: Sore throat at swallowing (0 – absent, 1 – mild, 2 – moderate, 3 – severe / pronounced); Sore throat at rest; Throat irritation at rest; Palatine tonsils hyperemia; Palatine tonsils edema); Patients self-assessment (VAS; 0-10)

- 2 visit (3rd±1 day): intermediate evaluation of the effectiveness of treatment - clarification of the patient's condition, the need to prescribe an antibiotic; evaluation by LTM Scale, patients self-assessment (VAS; 0-10)
- 3 visit: intermediate evaluation of the effectiveness of treatment (day 5-day ±1) via telephone (or visit if necessary); patients self-assessment (VAS; 0-10)
- 4 visit: final (10th day ±1 day). Evaluation by LTM Scale (0-15), patients self-assessment (VAS; 0-10)
- 5 Follow up; day 28: evaluation of the long-term effects of treatment
- - An unscheduled visit can be made if the patient's condition worsens (according to the patient and / or the researcher, including if the symptoms of the disease persist or worsen, including but not limited to an increase in the temperature in the armpit above 38.0 ° C at the 3rd and / or subsequent days of treatment).
- The total duration of the treatment: 10 days
- The total duration of the study for one patient is not longer than 38 days.

Any unscheduled visit may be carried out in case of worsening of the patient's condition (at patient's and/or investigator's opinion), including persistence or aggravation of the disease symptoms.

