Checks for general well-being (AE-checks), checks of restrictions and medication will be performed.

The investigator will estimate indicators for prescription of antibiotics and will decide whether a patient will remain on the study treatment or not. If an antibiotic agent is prescribed, details will be documented and the patient will be instructed about the mode of administration. Intake of

antibiotic drug will be documented in the CRF. Patients with intake of antibiotics will be evaluated separately. At the discretion of the investigator the patient may be advised not to take IMP anymore. If so, this will be documented as well.

Self-assessment of the patient's throat pain by him/herself and (or) his/her parent(s) using a visual analogue scale (VAS) is performed afterwards. Moreover, forms for VAS assessment will be handed over to the patient. The patient will have to assess his/her sore throat every study day until visit 4 on study day 10±1.

10.3 Interim evaluation of treatment efficacy- Visit 3

Visit 3 (V3) will be performed on day 5 ±1 by a telephone call.

Intermediate evaluation of the effectiveness of treatment (day 5-day ±1) via telephone (or visit if necessary); patients self-assessment (VAS; 0-10)

10.4 Treatment efficacy, end of Reference treatment - Visit 4

At visit 4 (V4) on day 10 ±1 the status of the disease will be again evaluated.

A physical examination of vital signs (blood pressure, pulse rate, body temperature (axillar)) will be performed. All physical examinations done at V1 including skin and visible mucosa, palpation of abdomen and lymph nodes, oropharyngoscopy will be repeated to assess the status of the tonsillitis.

Again, objective symptoms included in the "Local Tonsillitis Manifestation Scale".

Checks for general well-being (AE-checks), checks of restrictions and medication will be performed.

Self-assessment of the patient's throat pain by him/herself and (or) his/her parent(s) using a visual analogue scale (VAS; 0-10 points) is performed. Forms of VAS assessment will be collected from the patient.

10.5 Treatment efficacy, end of treatment - Visit 5

Visit 5 (V5) will be performed on day 28 by a telephone call (for both the groups).

Checks for general well-being (AE-checks), checks of restrictions and medication will be performed.

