12.2.1 Analysis sets

Full Analysis Set (FAS)

The FAS consists of all randomized patients with at least one documented application of IMP and with at least one observed post-baseline value.

Per Protocol Set (PPS)

The PPS consists of all patients of the FAS without major protocol deviations. The evaluation of protocol deviations and whether they lead to the exclusion of a patient from the PPS will be performed during data review of the study.

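### Section 9.4.1 allows an unblinded investigator to take a child out of the whole trial for events that are, or usually imply, primary failure, and requires no Visit 4 or day-28 follow-up afterwards

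*Protocol*

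**What the plan says.** The trial is open (Protocol 8.4). Section 9.4.1 lists eleven grounds on which the investigator can withdraw a child from the trial, not merely from treatment. One is "Appearance of an exclusion criterion, which concerns the safety of the patient in the opinion of the investigator". The exclusion criteria in 9.3 include "Indication for immediate initiation of systemic antibiotic therapy", purulent complications and severe general condition.

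The synopsis makes "Absence of indications for prescribing antibacterial therapy" part of the definition of effective treatment and classes every child who falls short of that definition as not effective.

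On withdrawal, 9.4.1 asks for the reason, the date and the last intake of study drug. It asks for no closing assessment, no Visit 4 and no day-28 call.

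Two other sections treat antibiotics as something that happens within the trial. Section 8.3.3 includes them in the reference treatment when indicated and adds "in case of prescription of antibiotics patients will be evaluated separately". Section 10.2 has the prescription documented, allows study drug to be stopped, and says "Patients with intake of antibiotics will be evaluated separately". Section 8.3.4 does not list antibiotics among the drugs that force withdrawal.

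The full analysis set (Protocol 12.2.1; SAP, Analysis sets) takes randomised patients who had an application of study drug and "with at least one observed post-baseline value". The primary endpoint text (Protocol 12.2.2; SAP, Primary endpoint) dichotomises the scores visit by visit and counts need for antibacterial therapy by treatment. It does not repeat the synopsis definition of failure.

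**The concern.** A child who develops an antibiotic indication has failed the primary endpoint, and the same event can be used to end that child's participation. The decision is discretionary and made with knowledge of the arm. Two investigators could handle the same child differently, one under 10.2 and one under 9.4.1, and both would comply.

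Two things are at stake. First, Visit 4 results are to be reported per visit, and the children missing from them could be mainly failures, in unequal numbers by arm. Second, Protocol 6.3 asks whether delaying antibiotics is safe at this age. The children in whom delay failed are the ones whose later course bears most on that question. Adverse event follow-up (11.2) covers only part of it, because 11.1.1 generally keeps worsening of the disease under study out of adverse event recording.

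**Working it through.** **Step 1. How far the withdrawal ground overlaps with failure.**
- Antibiotic indication: failure by definition (synopsis, Efficacy endpoints).
- Purulent complication or severe general condition: not failure by definition, but either would usually bring an antibiotic indication.
- Suspected mononucleosis, hypersensitivity, or a newly recognised risk disease: not failure by definition.

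The overlap is therefore with some of the criteria in 9.3, and not with the 9.4.1 list as a whole, which also covers consent, pregnancy and compliance.

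**Step 2. What is already protected.** The visit that prompts withdrawal will usually give a post-baseline value. Section 8.5 says "Any unscheduled visit may be carried out in case of worsening of the patient's condition", and the synopsis provides for "Axillary temperature assessment at each visit including any unscheduled visits". If the synopsis definition is then applied, the child counts as a failure in the randomised arm and the bias in the overall success rate is zero.

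**Step 3. What is not protected.**
- Visit 4 scores and the day-28 contact (9.4.1 is silent).
- The scoring of visits after withdrawal (Protocol 12.2.2 and the SAP give no rule).
- Whether separately evaluated antibiotic users also stay in the main comparison (8.3.3 and 10.2 do not say).
- Control children in the full analysis set. Membership needs an application of study drug, and Protocol 8.3 names only Imupret as that drug.
- Timing. Analysis specifications are to be set after the database is closed (Protocol 12.2; SAP, Statistical evaluation).

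**Step 4. The plan's own figure.** Inputs from Table 1 of the synopsis: z values 1.96 and 0.84, success 0.75 and 0.90, difference 0.15.

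n = (1.96 + 0.84)² × [0.75 × 0.25 + 0.90 × 0.10] / 0.15² = 7.84 × 0.2775 / 0.0225 = 96.7, so 97 per group.

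The departures entry of 3 brings this to 100, whether read as 97 + 3 or as 97 / 0.97. The sample size reproduces and is not at issue.

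**Step 5. Illustration of one reading only: withdrawn failures leave the denominator.** Assumptions: 100 per arm; every removed child is a failure; pooled z test at two-sided 0.05, a test the documents do not name; exact binomial enumeration. The numbers removed are assumed, since the documents give no withdrawal rate. The 3 departures per arm in Table 1 are a general allowance and serve only as a scale.

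No true effect, 75% success in both arms:

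| Failures removed (Imupret, control) | Apparent difference, Imupret minus control (points) | Chance of significance favouring Imupret |
|---|---|---|
| 0, 0 | 0 | 2.5% |
| 1, 0 | +0.8 | 3.4% |
| 3, 3 | 0 | 3.2% |
| 3, 1 | +1.6 | 5.0% |
| 3, 0 | +2.3 | 6.2% |
| 5, 0 | +3.9 | 10.7% |
| 10, 0 | +8.3 | 31.7% |
| 0, 1 | −0.8 | 1.9% |
| 0, 3 | −2.3 | 1.1% |

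The 3, 0 row can be checked at expected counts: 75/97 − 75/100 = 0.773 − 0.750 = 2.3 points. The 0, 3 row is its mirror image.

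Table 1 rates, 90% against 75%: with no removal the chance of significance is 81.6%. Removing 1 Imupret and 3 control failures shrinks the difference from 15.0 to 13.6 points and the chance of significance to 74.5%.

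**The case against.** The strongest reply is that 9.4.1 says nothing about denominators. Under the synopsis a withdrawn failure is still a failure. Any loss from the main comparison would come from the undefined separate evaluation of antibiotic users and from specifications set after database closure, and both exist whether or not anyone is withdrawn. This stands, and it is why the table above cannot be read as the effect of 9.4.1 itself.

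Second, 8.3.3 and 10.2 give a specific in-trial route for antibiotic cases, and the criterion in 9.3 was written for entry. This also stands: withdrawal is possible, not mandatory. But 9.4.1 names exclusion criteria as a ground for withdrawal and does not refer to that route.

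Third, a Visit 4 score cannot change the class of a child who has already failed, and the day-28 call carries no tonsillitis score. This is true for an overall classification. It is not true for per-visit Visit 4 results, and the call is a scheduled safety contact in a trial that asks about safety.

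Fourth, discretion to protect a patient is normal, and the trial calls itself exploratory. Both are fair. The fix leaves treatment decisions untouched, and the trial still randomises and compares arms.

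A reader might infer that 9.4.1 inflates the false-positive rate in favour of Imupret. The documents do not support that. They neither remove withdrawn children from the denominator nor suggest in which arm withdrawals would be more frequent. Removal from control alone would work against Imupret.

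**Conclusion.** The point holds as a minor one. An unblinded, discretionary exit from the whole trial overlaps with primary failure, and nothing requires the child to be seen at Visit 4 or called on day 28. Visit 4 results and the safety follow-up of delayed antibiotics can therefore lose failures selectively.

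For the overall success rate, the bias is zero if the synopsis definition is applied to all randomised children. If failures instead leave the denominator, the size and direction are unknown, because both depend on a withdrawal count and an imbalance that the documents do not give.

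Two stronger readings should be avoided: that the withdrawal grounds as a whole coincide with failure, and that the full analysis set already protects both arms. The first is true only of some exclusion criteria. The second is not established for control children, given the requirement of an application of study drug.

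**What to change.** In Protocol 9.4.1, state that an antibiotic indication, purulent complication or hospitalisation indication arising after randomisation may stop Imupret but is not in itself a reason to leave the trial. Such a child is followed to Visit 4 and the day-28 call unless consent is withdrawn. Cross-refer to 8.3.3 and 10.2.

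In the SAP, before the database is closed, state that:
- every randomised child in either arm with an antibiotic indication after randomisation stays in the main comparison, with no requirement of an Imupret application;
- that child is scored not effective at that visit and all later ones;
- separate evaluation of antibiotic users is an additional summary and does not replace their place in the main comparison.

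The cost is a few sentences, a small change to the full analysis set wording, and a little extra follow-up at contacts already scheduled. Reported Visit 4 success may be slightly lower, because failures that might have gone unassessed are counted. Treatment freedom and the right to withdraw consent are unaffected.

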9.4.2 Replacements

Patients withdrawn from the trial after randomization, regardless of the reason for withdrawal, will not be replaced.

9.4.3 Premature termination of the trial

Premature termination of a clinical trial may occur upon decision of the sponsor, the Principal Investigator, by request of an authority or because of withdrawal of positive vote by the responsible ethics committee. Furthermore, the Principal Investigator / sponsor has the right to close participating center(s) of the trial, at any time, although this can occur only after consultation between involved parties.

